## 7.7.3 General approach to analysis for the cohort study

### 7.7.3.1 Statistical methods

An interim report will be provided annually to the Sponsor containing descriptive data only on characteristics of women enrolled in the study and cumulative study outcomes. No statistical comparisons are planned for the annual interim reports. The final report will be provided to the Sponsor after closure of the study and further detailed in the SAP.

#### 7.7.3.1.1 Analyses of the primary outcome

The primary outcome of interest, i.e. major structural defects, will be estimated in each cohort as a proportion (95% CI) using two denominators i) pregnancies ending in at least one live born infant and ii) pregnancies ending in at least one live born infant, stillborn, spontaneous abortion or elective termination. Data will also be presented by gestational timing of exposure.

For the primary endpoint, the exposure of interest is siponimod exposure at any time from the 4th day post the first day of the LMP prior to conception to the end of the first trimester, whether or not there is continued exposure to siponimod in the second or third trimesters. The primary comparison will be the rate of major structural defects between the siponimod-exposed group and comparison group 1 (disease-matched comparison group) among pregnancies resulting in at least one live born infant. A point estimate of the crude (i.e. unadjusted) risk ratio (RR) of the siponimod-exposed group versus comparison group 1, as well as its 95% confidence interval (CI) will be computed.

The same analysis will be repeated using the second numerator and denominator encompassing pregnancies ending in at least one live births, stillbirth, spontaneous abortion or elective termination, but excluding those lost-to-follow-up.

Due to the observational nature of the study, the above crude estimate of RR will be further adjusted for potential confounders (Rosenbaum, 2002), provided that there are sufficient numbers of events. A complete list of potential confounders, which includes but not limited to the baseline characteristics, will be provided in the SAP for each outcome prior to the final analysis, based on scientific knowledge including literature review.

As a primary approach, following Levenson and Yue, 2013, all potential confounders will be accounted for in the propensity score model.

As a secondary approach, a sensitivity analysis will be considered and the following three criteria applied to identify confounders (Xu et al, 2018, Greenland et al, 1999): 1) by assessing each considered variable in a logistic regression model containing the exposure variable and the outcome variable to determine if inclusion of that single covariate changes the estimate of the odds ratio for exposure by 10% or more; 2) standardized mean differences (SMD) greater than 0.1; 3) association with the outcome with p-value < 0.2 in the unexposed cohort (comparison group 2). Care will be taken not to include those variables that are strongly associated with the exposure variable but only weakly associated with the outcome variable (e.g. instrument like variables) (Brookhart et al, 2006). The confounders identified above will be used to build the propensity score (PS) for exposure (Rosenbaum, 2002).

Balance in the covariate distributions before and after weighting will be assessed by providing the standardized mean differences of all covariates.

The primary analysis will be performed using the PS via inverse probability weighting (IPW).

As secondary analysis, the PS will be used in the so-called outcomes regression (Xu et al, 2018, Vansteelandt et al, 2014), i.e. a logistic regression model will be fitted with major structural defect (Y) as outcome, and exposure (A) and logit of propensity score (L) as regressors. In a second step, standardization will be performed to obtain the estimated causal risk ratio (Hernan and Robins, 2019). The CI for the causal risk ratio will be obtained by bootstrap.

Several sensitivity analyses will be performed for the primary outcome of major structural birth defects. One analysis will exclude those defects thought to be of chromosomal or genetic origin. Exposure to a known human teratogen is already included in the list of potential confounders for the siponimod-exposed group vs. comparison group 1. However, in the case where there are insufficient number of events to consider regression adjustment, a sensitivity analysis will be performed excluding participants with exposure to known teratogens in the siponimod-exposed group and comparison group 1 to address this potential confounder.

As prior knowledge from prenatal ultrasound or diagnostic testing could introduce bias, a sensitivity analysis for the primary outcome of major structural birth defects will be performed stratified on prenatal testing prior to enrollment (yes/no). A second sensitivity analysis is also planned stratified on any abnormal prenatal ultrasound or diagnostic testing prior to enrollment (yes/no). These analyses are described in detail in the SAP.

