#### **Cohort 2: Disease-Matched Comparison Cohort (Comparison Group 1)**

1. Pregnant women

2. Diagnosed with MS, with the indication validated by medical records when possible
3. May or may not have taken another medication for MS in the current pregnancy (see exclusionary medications [Section 7.2.2.2](#))
4. Agree to the conditions and requirements of the study including the interview schedule, release of medical records, the dysmorphology examination of live born infants, and the ASQ in live born children

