### **Cohort 3: Healthy Comparison Cohort (Comparison Group 2):**

1. Pregnant women
2. Agree to the conditions and requirements of the study including the interview schedule, release of medical records, the dysmorphology examination of live born infants, and the ASQ in live born children

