### **Cohort 3: Healthy Comparison Cohort (Comparison Group 2):**

1. Exposure to Kesimpta 166 days before or to siponimod any time from the 4th day post first day of LMP prior to conception up to and including end of pregnancy
2. Women who have a diagnosis of a MS or a siponimod approved indication
3. Women who have a current diagnosis of any autoimmune disease
4. Women who have first contact with the project after prenatal diagnosis of any major structural defect
5. Women who have enrolled in the siponimod cohort or Kesimpta cohort study with a previous pregnancy
6. Women treated with Mayzent or Kesimpta for non-MS indication
7. Retrospective enrollment after the outcome of pregnancy is known (i.e. the pregnancy has ended prior to enrollment)
8. Results of a diagnostic test are positive for a major structural defect prior to enrollment. However, women who have had any normal or abnormal prenatal screening or diagnostic test prior to enrollment are eligible as long as the test result does not indicate a major structural defect.
9. Women exposed to a known human teratogen during pregnancy as confirmed by the OTIS Research Center

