### **7.2.2.4 Analysis populations**

The Registry will collect and follow-up on reports of all types (i.e., retrospective, exposure after first trimester only, off-label indication, etc.: see [Section 7.2.2.3](#)) involving pregnancy exposure to siponimod; however, the core of the Registry will be a prospective cohort study designed to ascertain and follow-up on pregnancy exposures to siponimod and to compare these outcomes to 2 internally-generated comparison groups and one external comparison group (Metropolitan Atlanta Congenital Defects Program, or MACDP).

- Comparison Group 1 consisting of diseased-matched pregnant women who have not been exposed to siponimod at any time from the 4th day post first day of LMP prior to conception up to and including the end of current pregnancy. This will be the primary comparison group.
- Note that this cohort will be common between this study and the Kesimpta-OTIS pregnancy registry sub-study (OMB157G2403). The first 125 eligible pregnancies after OMB157G2403 protocol approval will be eligible for inclusion in both studies.
  - Comparison Group 2 consisting of pregnant women who contact the study directly or who are referred to the study, and who do not have MS, have not been exposed to a known human teratogen, and have not taken siponimod in pregnancy. This will be a secondary comparison group.
- Note that this cohort will be common between this study and the Kesimpta-OTIS pregnancy registry sub-study (OMB157G2403). The first 125 eligible pregnancies after OMB157G2403 protocol approval will be eligible for inclusion in both studies.

Based on previous OTIS experience, it is estimated that Comparison Group 2 will be similar to the exposed and primary comparison group on key demographics such as maternal age, socioeconomic status and race/ethnic distribution. However, differences between the cohorts for these demographic factors will be monitored in the annual interim reports and, should they occur, will be addressed in future recruitment efforts and in the statistical analysis phase of the study through methods such as adjustment (to be detailed in the SAP).

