Socioeconomic Category	Confounder	Maternal report	Hollingshead Socioeconomic Category based on maternal and paternal occupation and education (1-5).
Maternal Height	Confounder	Maternal report	Maternal height (cm).
Maternal Pre-pregnancy body weight	Confounder	Maternal report Medical record	Maternal pre-pregnancy body weight (kg) (confirm with medical record).
Maternal Pre-pregnancy BMI	Confounder	Maternal report	Maternal pre-pregnancy BMI (<18.5, 18.5-24.9, 25-29.9, >=30).
Number of times pregnant	Confounder	Maternal report Medical record	Number of times ever pregnant (1, 2-3, 4-5, >=6) (confirm with medical record).
Previous live birth or stillbirth deliveries	Confounder	Maternal report Medical record	Number of previous live birth or stillbirth deliveries (0, 1-2, 3-4, >=5) (confirm with medical record).

Variable	Role	Data source(s)	Operational Definition
Previous pregnancies ending in spontaneous abortion	Confounder	Maternal report Medical record	Number of previous pregnancies ending in spontaneous abortion (0, 1, 2, >=3) (confirm with medical record).
Previous pregnancies ending in elective termination	Confounder	Maternal report Medical record	Number of previous pregnancies ending in elective termination (0, 1, 2, >=3) (confirm with medical record).
Gestational age	Confounder	Maternal report Medical record	Weeks of pregnancy at time of enrollment, continuous and categorical (<13, 13-19.9, >=20): gestational age is calculated from the first date of LMP.
Referral source	Confounder	Maternal report	Source options: Sponsor, OTIS service, HCP, Internet, Other.
Geographic area of residence	Confounder	Maternal report	Geographic area of residence (e.g., US, Canada).
Disease Symptom/Severity measures	Confounder	Maternal report	Disease Symptom/Severity measures (exposed and disease-matched cohorts only).
Prenatal, Multivitamin, or Folic acid	Confounder	Maternal report	Prenatal, Multivitamin or Folic Acid supplement use by timing (began prior to conception, post-conception only, not taken at all).
Alcohol use in pregnancy	Confounder	Maternal report	Yes/No. Dose and frequency are captured.
Tobacco use in pregnancy	Confounder	Maternal report	Yes/No. Dose and frequency are captured.

Variable	Role	Data source(s)	Operational Definition

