#### **7.7.3.2 Missing data**

Missing values typically occur in less than 5% of the cases for any single covariate. They are assumed to be missing at random. When there are missing values in any of the selected confounders, multiple imputation (MI) will be conducted, using the R package MICE (multivariate imputation by chained equations) (van Buuren and Groothuis-Oudshoorn, 2011). MI will be conducted for missing data using the entire dataset, i.e., on all cohorts combined.

For the outcome of SAB, for some cases the exact date of SAB might be unknown, and instead a window for possible SAB time is available. This is known as interval censored data, and can also be handled using MI (Pan, 2000). An exact SAB time will be imputed by sampling uniformly from the corresponding time window.

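### Criterion 3 of the sensitivity confounder screen is run in the healthy cohort instead of the disease-matched cohort, so it cannot be evaluated for the MS-specific covariates or for teratogen exposure

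*Protocol*

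**What the plan says.** **Which comparison is primary.** Section 7.7.3.1.1 states: "The primary comparison will be the rate of major structural defects between the siponimod-exposed group and comparison group 1 (disease-matched comparison group"). Section 7.2.2.4 says of the disease-matched women: "This will be the primary comparison group". The healthy women are a secondary comparison group.

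**How the cohorts are labelled.** The eligibility headings in 7.2.2.1 read "Cohort 2: Disease-Matched Comparison Cohort (Comparison Group 1") and "Cohort 3: Healthy Comparison Cohort (Comparison Group 2"). Cohort 2 is therefore comparison group 1, and Cohort 3 is comparison group 2.

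**How confounders are handled.** In the primary approach of 7.7.3.1.1 every potential confounder goes into the propensity score, and the primary analysis weights by the inverse of that score. A secondary approach, labelled a sensitivity analysis, selects confounders by three criteria: (1) a change of 10% or more in the exposure odds ratio, (2) a standardized mean difference above 0.1, and (3) "association with the outcome with p-value < 0.2 in the unexposed cohort (comparison group 2"). The variables selected build that analysis's propensity score. The section does not say whether a variable must meet all three criteria or any one.

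**What exists in the healthy cohort.** The Cohort 3 exclusions in 7.2.2.2 include "Women who have a diagnosis of a MS or a siponimod approved indication" and exposure to a known human teratogen. Table 7-1 lists as confounders "Disease Symptom/Severity measures (exposed and disease-matched cohorts only"), years since diagnosis, treatment history for the indicated disease, and known-teratogen exposure.

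**Missing data.** Section 7.7.3.2 says: "MI will be conducted for missing data using the entire dataset, i.e., on all cohorts combined". It assumes missingness at random and expects under 5% missing for any single covariate.

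**The concern.** A test of covariate–outcome association among unexposed women is meant to show which variables predict the outcome in the reference population of the comparison. For exposed versus disease-matched women, that population is Cohort 2. As written, the test is run in women without MS.

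The variables most affected are ones the protocol itself regards as important. Section 7.9 names age and disability as possible channelling factors and says the disease-matched women may have milder disease than the exposed women. Section 7.4.3.1 collects severity specifically to assess confounding and effect modification. Section 7.7.3.1.1 names teratogen exposure as a potential confounder for exposed versus comparison group 1, yet screens it in a cohort where it cannot vary.

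At stake is the content of the sensitivity propensity score. A sensitivity analysis that leaves out severity, duration, treatment history and teratogen exposure because of a cohort label would be hard to interpret beside the primary result. Section 7.7.3.1.2 carries the same propensity-score methods over to secondary outcomes, so the label travels with them.

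**Working it through.** **Step 1. Can criterion 3 be evaluated?** The Table 7-1 confounders at issue, taken against the cohort definitions in 7.2.2:

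| Confounder | Cohort 2 (group 1) | Cohort 3 (group 2) |
|---|---|---|
| MS severity measures | collected | not collected |
| Years since diagnosis | defined | undefined (MS excluded) |
| MS treatment history | defined | undefined (MS excluded) |
| Known-teratogen exposure | can vary | constant (exposure excluded) |

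For the first three there is no covariate value to relate to the outcome. For the fourth the covariate has one level and no association can be estimated. For the remaining covariates, such as age, BMI and tobacco, criterion 3 can be computed but describes women without MS.

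**Step 2. What follows for the screen?** Criteria 1 and 2 are not tied to the healthy cohort and can be computed in Cohorts 1 and 2.

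- If all three criteria must hold, the four variables cannot qualify and are left out of the sensitivity propensity score.
- If any one is enough, they can still enter through criterion 1 or 2, and criterion 3 adds nothing for them.

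**Step 3. How much would the corrected criterion deliver?**

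Inputs from 7.5.1: 289 women per cohort; 10% spontaneous abortion or stillbirth, 5% elective abortion, 5% lost to follow-up; baseline major-defect rate 3%.

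- Live-birth pregnancies per cohort: 289 × (1 − 0.10 − 0.05 − 0.05) = 231.2. The protocol's 231 is reproduced.
- Expected events in a comparison cohort: 231 × 0.03 = 6.93. The binomial 95% range is 2 to 12 events. The expectation is the same in Cohorts 2 and 3.

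The chance that a binary covariate passes p < 0.2 was simulated for one cohort of 231 at 3% overall risk (two-sided Fisher test, 4,000 runs per setting). The covariate prevalences (30% and 50%) and the covariate–outcome risk ratios are assumptions, not protocol figures.

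| Covariate–outcome risk ratio | Prevalence 30% | Prevalence 50% |
|---|---|---|
| 1 | 13.4% | 12.7% |
| 1.5 | 21.5% | 17.5% |
| 2 | 32.5% | 27.7% |
| 3 | 52.8% | 44.9% |

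Moving the test to Cohort 2 makes it computable. Even so, a covariate that doubles the risk would be picked up in only about 28–32% of studies, against about 13% for a covariate with no effect.

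**The case against.** **The primary analysis does not use the screen.** This stands. A reader might infer that the main confounders of the primary comparison go uncontrolled. The text does not support that: the primary propensity score takes all potential confounders without selection.

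**It may be a slip of label.** Cohort 2 and comparison group 2 are easily confused, and the author may have meant Cohort 2. This is plausible, but the protocol defines the term consistently elsewhere, and an analyst following the text would use the healthy women. The label would be right for exposed versus healthy, but the criterion is stated once, in a passage whose primary comparison is with group 1.

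**The MS variables are not necessarily lost.** This also stands. Criteria 1 and 2 remain available, and exclusion follows only if all three criteria are required.

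**The stronger reading on imputation.** A reader might infer from the pooled imputation rule that MS severity would be invented for every healthy woman, and might set 289/867 = 33.3% undefined values against the expected under 5%. Section 7.7.3.2 does not say that values which do not apply count as missing, or that they will be imputed. The under-5% expectation fits better with their not being counted, and 33.3% is simply the healthy cohort's share of enrolment. Healthy women are not in the exposed versus group 1 estimate, so imputed values could reach it only as predictors of other covariates. The treatment of such cells is mainly a matter for the SAP.

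**No ranking of confounders is shown.** Section 7.9 raises age, disability and severity as possibilities, and section 5 says maternal disease is not known to be a risk. Calling the MS variables the strongest confounders would go beyond the document.

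**Conclusion.** Criterion 3 is wrong as written for the primary comparison. It names a cohort in which four listed confounders (MS severity, years since diagnosis, MS treatment history, known-teratogen exposure) cannot be tested, and which is the wrong reference population for the rest.

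The consequence is confined to the sensitivity propensity score and to secondary outcomes that reuse the method. It ranges from losing all four variables, if every criterion must be met, to little effect, if any one is enough; the protocol leaves this open. The primary inverse-probability-weighted estimate does not depend on it.

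With about 7 expected events in either comparison cohort, the correction makes the criterion coherent but not powerful. That figure rests on the protocol's planning assumptions (231 live-birth pregnancies, 3% baseline), and the pass probabilities rest on the assumed covariate prevalences and risk ratios. The imputation point is a clarification only. The correction should be made because it is specific and nearly free.

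**What to change.** 1. In 7.7.3.1.1, criterion 3, replace comparison group 2 by comparison group 1 for the primary comparison, and state that each comparison uses its own unexposed cohort (Cohort 2 against disease-matched women, Cohort 3 against healthy women).
2. In the same paragraph, state whether the three criteria combine by AND or by OR.
3. As a minor clarification in 7.7.3.2, state that MS-only covariates are not applicable in Cohort 3 and are imputed only within Cohorts 1 and 2.

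The cost is a few sentences and at most one additional imputation run. Data collection, sample size and the primary analysis do not change.

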## Study size

The prospective cohort study target sample size is 289 pregnant women who have been exposed to siponimod in pregnancy (i.e. on or any time after the 4th day post first day of the LMP prior to conception), for MS, 289 pregnant women diagnosed with MS not exposed to siponimod during pregnancy (primary comparison group/comparison group 1), and 289 healthy women i.e. women who are not diagnosed with MS, or any other autoimmune disease, and without exposure to siponimod, or any known human teratogen during pregnancy (secondary comparison group/comparison group 2).

The current sample size provides 80% power to detect a risk ratio of approximately 3.0 or greater in major structural defects with reference to the baseline prevalence of 2.8% in the Atlanta metropolitan area ([CDC 2017](#)).

Up to an additional 50 women will be enrolled in an exposure series group. This is a group of women with exposure to siponimod during pregnancy, but who do not meet eligibility criteria for the siponimod-exposed cohort group (e.g. retrospective cases would be in this group).

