### 7.5.1 Determination of sample size

The sample size for this study is not only based on the statistical considerations to address the question of interest but also takes into account the feasibility aspects, prior experience and available literature ([Krueger et al 2017](#)) on conduct of pregnancy registries in the MS disease area.

In the three cohorts, approximately 867 pregnant women will be enrolled in US and Canada with a ratio of 1:1:1.

Based on previous experience with MotherToBaby/OTIS Pregnancy Studies, it is estimated that subjects will be an average of 7-10 weeks post-LMP at the time of enrollment. Given this mean gestational timing at enrollment, the anticipated spontaneous abortion/stillbirth rate is 10%, the estimated elective abortion rate is 5%, and the estimated lost to follow-up rate is 5% ([Chambers et al, 2016](#)). This will result in known outcomes for approximately 273 pregnancies in each cohort, including 231 pregnancies with at least one live born infant in each cohort at the end of recruitment.

Baseline rates of major structural birth defects, specific patterns of three or more minor structural defects, premature delivery, and small for gestational age are based on previous MotherToBaby/ OTIS studies and on general population data. Rates of spontaneous abortion in the general population are 15-20% ([Avalos AL, et al 2012](#), and [Magnus et al 2019](#)). However, since women do not typically enroll in pregnancy registries until after 7-8 weeks' gestation when the highest risk of spontaneous abortion has passed, the baseline estimate is drawn from previous OTIS studies. [Table 7-4](#) gives the minimum detectable effect sizes with 80% power (two-sided significance level 0.05, except as noted below for pattern of minor structural defects), for the comparisons described above. If the disease-matched comparison and the healthy comparison groups are comparable, then consideration will be given to pooling data in the two comparisons cohorts for analysis, as shown in [Table 7-5](#). The current sample size provides 80% power to detect a risk ratio of approximately 4.4 or greater in major structural defects compared to the baseline prevalence of 3% in the comparison groups. This is consistent with the population prevalence of major structural defects of 2.8% in the Atlanta metropolitan area ([CDC 2017](#)).

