**Table 7-4 Sample Size and Detectable Effect Size with 80% Power for Comparison of Exposed Cohort 1 to Unexposed Cohort 2**

Endpoint	N per group	Rate in comparison group	Relative risk	Power
Major structural defects b	231	3%	3.0	80%
Specific pattern of 3 or more minor structural defects	231	1%	4.6	80% c
Spontaneous abortion/still birth	259	10%	1.9	80%

Endpoint	N per group	Rate in comparison group	Relative risk	Power
Preterm delivery	231	10%	1.9	80%
Small for gestational age	231	10%	1.9	80%

aAll tests are two-sided with alpha = 0.05, based on Fisher's exact test, unless specified otherwise. Calculations conducted using R.

bPrimary endpoint; among livebirths.

cOne-sided

**Table 7-5 Sample Size and Detectable Effect Size with 80% Power for Comparison of Exposed Cohort 1 to Unexposed Cohorts 2 and 3 Combined**

Endpoint	N in exposed group	N in comparison group	Rate in comparison group	Relative risk	Power
Major structural defects b	231	462	3%	2.7	80%
Specific pattern of 3 or more minor structural defects	231	462	1%	4.0	80% c
Spontaneous abortion/still birth	259	518	10%	1.7	80%
Preterm delivery	231	462	10%	1.8	80%
Small for gestational age	231	462	10%	1.8	80%

aAll tests are two-sided with alpha = 0.05, based on Fisher's exact test, unless specified otherwise. Calculations conducted using R.

bPrimary endpoint; among livebirths.

cOne-sided

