Given the Phase III data supporting the siponimod approval for relapsing forms of MS was generated in the SPMS population, as reflected in the clinical studies section of the FDA approved labelling, it may transpire that siponimod is more likely to be prescribed to patients

who are older and with higher disability. Thus there is potential for channeling bias. To the extent that factors such as age and disability differ in exposed and comparison cohorts, these will be considered in adjusted analyses.

It is possible that women in the disease comparison group may have less severe disease than those who enroll in the siponimod exposed group. It is also possible that women in the siponimod exposed group will enroll earlier in pregnancy than either of the comparison groups. The study will monitor disease severity and gestational age at enrollment and discuss any modifications needed in recruitment strategies as the study progresses. Further, all three cohorts rely on volunteers and may not represent the entire population of exposed and unexposed women.

Although all possible efforts will be made to retain participants in the registry or follow up with their healthcare providers, some participants will be lost during follow up. It could be possible that participants lost during follow up and with missing data on outcomes may be different compared to those with complete follow up data. In previous OTIS studies, lost-to-follow-up rates have been low, typically <5%. However, the characteristics of women lost to follow up will be compared to those who are retained in order to understand the direction and magnitude of the bias due to loss to follow up.

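### The stated 80% power for a risk ratio of 3.0 belongs to a crude, unweighted comparison; the primary analysis is inverse-probability weighted, and no allowance is made for the precision that weighting costs

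*Protocol*

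**What the plan says.** **Power.** The Abstract (Study size) states "The current sample size provides 80% power to detect a risk ratio of approximately 3.0 or greater in major structural defects". Table 7-4 gives the same risk ratio for the primary endpoint among live births, with 231 per group and 3% in the comparison cohort. Its footnote says "All tests are two-sided with alpha = 0.05, based on Fisher's exact test, unless specified otherwise".

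**Analysed number.** Section 7.5.1 goes from 289 enrolled to 231 per cohort by deducting 10% for spontaneous abortion or stillbirth, 5% for elective termination and 5% for loss to follow-up. It deducts nothing else.

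**Analysis.** Section 7.7.3.1.1 first plans a crude risk ratio with a 95% confidence interval against the disease-matched cohort. It then plans adjustment if there are enough events. For the primary approach, "all potential confounders will be accounted for in the propensity score model", and "The primary analysis will be performed using the PS via inverse probability weighting (IPW".

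**Imbalance.** Section 7.9 says siponimod may turn out to be prescribed to older and more disabled patients, and concludes "Thus there is potential for channeling bias". It adds that the disease-matched women may have milder disease. It puts no size on either.

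**The concern.** The design whose power is stated is not the design that is analysed. Weighting by the inverse of an estimated propensity score reduces the effective number of pregnancies, more so as the exposed and comparison cohorts differ. Table 7-4 treats all 231 per group as carrying full information.

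This is a post-marketing safety requirement on a teratogenicity question. If the weighted risk ratio shows no clear increase, its strength will be judged against the stated chance of detecting a tripling of major defects. If that chance was computed for a different estimator, the reassurance is overstated. Events are few: 231 × 0.03 ≈ 7 expected in the comparison cohort and 231 × 0.09 ≈ 21 in the exposed cohort at a risk ratio of 3.0, about 28 in all.

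**Working it through.** **Inputs from the protocol.** Section 7.5.1: 289 × 0.80 = 231.2, so 231 per cohort; comparison rate 3%; 1:1 for the primary comparison. Table 7-4: risk ratio 3.0 (so 9% exposed), two-sided alpha 0.05.

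**Step 1. Reproduce the stated 80%.** Arcsine formula: power = Φ(h·√(n/2) − 1.960), with h = 2(asin√0.09 − asin√0.03).
- h = 2(0.3047 − 0.1741) = 0.2612
- h·√(231/2) = 0.2612 × 10.747 = 2.807
- Φ(2.807 − 1.960) = Φ(0.847) = **80.2%**

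The smallest risk ratio this formula detects with 80% power is 2.995. The formula also reproduces the printed risk ratios in the other rows of Tables 7-4 and 7-5 after rounding. The printed power is therefore a crude two-proportion figure.

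**Step 2. Apply the test the footnote names.** Exact enumeration of the two-sided Fisher's exact test at 231 v 231, 3% v 9%, gives **74.0%**. At a risk ratio of 3.2 it gives 80.8%. So the printed figure and the named test disagree before any weighting.

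**Step 3. Allow for weighting.** The protocol gives no ESS, so the fractions below are assumptions. In the arcsine formula, n = 231 is multiplied by the ESS fraction, which multiplies 2.807 by its square root (for example √0.80 × 2.807 = 2.511; Φ(2.511 − 1.960) = 70.9%). For Fisher, the exact calculation is repeated at the reduced n.

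| Assumed ESS | n per group | Arcsine power | Detectable RR at 80% (arcsine) | Fisher power |
|---|---|---|---|---|
| 100% | 231 | 80.2% | 3.0 | 74.0% |
| 90% | 208 | 75.9% | 3.1 | 68.5% |
| 80% | 185 | 70.9% | 3.3 | 62.2% |
| 70% | 162 | 65.1% | 3.5 | 54.7% |

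**Step 4. Simulate the weighted analysis.** Set-up: 231 per group, 3% v 9%, logistic propensity score, normalised weights, Wald test on the log risk ratio. The 26 covariates match the number of variables labelled as confounders in Table 7-1. The standardised mean differences (SMDs) are assumed, and the covariates are unrelated to outcome.

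| Assumed imbalance | ESS | Power, weights treated as fixed | Power, allowing for the estimated score |
|---|---|---|---|
| None | 94% | 74.9% | 77.7% |
| All SMDs 0.1 | 86% | 72.1% | 75.2% |
| 0.5 / 0.3 / 0.3, rest 0 | 80% | 68.8% | 72.6% |
| 0.5 / 0.3 / 0.3, rest 0.1 | 73% | 67.5% | 71.6% |

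The crude log-risk-ratio test in the same runs has 77.5–78.3%. The fair cost of weighting is the gap between that and the last column: from about 0 points with balanced covariates to 78.3 − 71.6 = 6.7 in the last row. Repeat runs put the upper end at about 8. The remaining 2 to 3 points below 80% come from the change of test, not from weighting. A smaller model with 10 covariates gave a similar picture: 77.5% with no imbalance and 71.0% at a composite SMD of 0.8, against 77.3% crude.

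**The case against.** The strongest reply has four parts.

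1. **Channelling is only a possibility.** A reader might infer that the weighted analysis has 67–75% power under channelling that the protocol expects. The document does not support this. Section 7.9 says only that channelling could occur and gives no size, and that range rests on assumed SMDs and an assumed set of 26 covariates. Section 7.7.3.1.1 leaves the confounder list to the SAP, and Table 7-1 contains overlapping items such as height, weight and BMI. The low end also treats the weights as fixed, which is conservative here and not prescribed. This part stands, so the loss is given only as an assumed range.

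2. **The crude risk ratio is also planned, and adjustment depends on having enough events.** True, and with about 7 expected comparator events the crude result may carry weight. But the analysis designated as primary is the weighted one. If it goes ahead, the printed power is not its power; if it does not, the planned primary analysis is not delivered.

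3. **The footnote shows that the calculation is unadjusted, and Section 7.9 admits limited power.** Both are fair. Neither tells the reader that the primary estimator is less precise, or by how much.

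4. **Arcsine figures would be wrong under a Fisher footnote.** This stands, and it shapes the fix: any added figures must use the same test as the table.

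**Conclusion.** The point holds in limited form. The 80% at a risk ratio of 3.0 describes a crude comparison at the full 231 v 231, and the protocol makes no allowance for weighting in its primary analysis. Two parts need no outside assumption: the mismatch between the powered and the primary analysis, and the gap between the printed 80% and the 74.0% of the named test.

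The size of the weighting loss does need an assumption. For ESS of 90%, 80% and 70%, power is about 76%, 71% and 65% (arcsine) or 69%, 62% and 55% (Fisher). Against a crude log-risk-ratio test, weighting alone costs roughly 0 to 8 points in simulation, with close to nothing lost if the cohorts are well balanced. It would go too far to conclude that the weighted analysis has any one particular power, or that enrolment must rise; Sections 7.5.1 and 7.9 say openly that the sample size also reflects feasibility.

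**What to change.** In Section 7.5.1, Table 7-4 and the Abstract:

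- State that the given power and the risk ratio of 3.0 apply to the crude, unweighted comparison only.
- Make the figure and the named test agree: either name the approximation that gives 80.2%, or keep Fisher's exact test and print what it gives (74.0% at a risk ratio of 3.0).
- Add power and detectable risk ratio for the weighted primary analysis at ESS of 90%, 80% and 70% of 231 per group, computed with that same test and labelled as assumptions.

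While editing Section 7.5.1, also reconcile its statement of "80% power to detect a risk ratio of approximately 4.4 or greater in major structural defects" with the 3.0 in Table 7-4 and the Abstract. At 4.4, Fisher power with 231 v 231 would be 98%, so the two cannot both describe 80% power.

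The cost is a few lines of text and table. Enrolment and analysis do not change. The downside is a less favourable stated power.
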